### Definition of Clinically Relevant Non-Major Bleeding Events

Clinically-relevant non-major bleeding is defined as overt bleeding not meeting the criteria for MB but that resulted, for example, in medical examination, intervention, or had clinical consequences for a subject.

### Definition of Minor Bleeding Events

Minor bleeding events are those that do not fulfill the criteria for MB or CRNMB (defined above), for example excess bruising, petechiae, gingival bleeding on brushing teeth.

#### 8.6.4. Stopping Rule for Potassium

In the event of confirmed potassium of  $\geq 6.0$  mmol/L or  $\geq 5.5$  mmol/L *with* new ECG changes consistent with hyperkalemia at any time during the study, dosing of a subject with Study Drug will be stopped permanently. The subject should stop any medications (e.g., ACE/ARB) or high K+ diet/supplements affecting potassium levels. Measure potassium frequently until documented to be  $< 5.5$  mmol/L. If there are ECG changes consistent with hyperkalemia or muscle weakness the subject should be admitted to the hospital. The Investigator may consider obtaining a nephrology consultation with consideration for dialysis to treat hyperkalemia. Additional consultation of the Investigator with the Sponsor Medical Monitor may be considered to individualize treatment plan.

#### 8.6.5. Stopping Rules for Blood Pressure

1. In the event of a confirmed BP measurement  $\leq 90$  mmHg (systolic) and/or the subject remains symptomatic (i.e., dizziness, light-headedness, clammy skin, fatigue, blurry vision) after instituting oral or IV hydration, Study Drug should be permanently discontinued, and the subject should be referred to urgent care or the emergency room.

Any other antihypertensives or other medications that could affect BP should be stopped, if feasible. The use of IV angiotensin II or vasopressors should be considered in subjects that remain symptomatic and are hemodynamically unstable. The subject will continue to be followed per protocol in the study. Follow-up for subjects that screen fail due to BP inclusion criteria (see Section 5.1) will not be necessary.

2. Should a subject experience a BP measurement  $> 180$  mmHg (systolic) or  $> 110$  mmHg (diastolic) a second measurement must be done within a 30-minute period. If the subject then experiences a second BP measurement  $> 180$  mmHg (systolic) or  $> 110$  mmHg (diastolic), they will then be withdrawn from further blinded, randomized treatment. Study Drug is to be permanently discontinued unless the hypertensive event is transient and dependent on reversible initiating factors (e.g., stressful event). The suitability of the subject for continued dosing will be determined by the Investigator in consultation with the Sponsor Medical Monitor after the subject's BP has normalized. Additional antihypertensive medication(s) may be added per Investigator and Sponsor Medical Monitor judgement if the subject has discontinued Study Drug. If the subject has not discontinued Study Drug, changes to the stable regimen of antihypertensives may result in withdrawal of the subject from the Treatment Period. The subject will continue to be followed per protocol in the study. Follow-up for subjects that screen fail due to BP inclusion criteria (see Section 5.1) will not be necessary.

**Table 7: Blood Pressure Monitoring and Stopping Rules Reference Table**

Confirmed Blood Pressure	Dosing	Additional Actions
SBP $\leq$ 90 mmHg* and/or subject is symptomatic (e.g., decreased oral intake, cold/flu, other illness).	Pause	Institute oral and/or IV hydration. If hypotension or symptoms of hypotension persist proceed to stopping rules below The suitability of the subject for continued dosing will be determined by the Investigator in consultation with the Sponsor Medical Monitor after the SBP has normalized and/or subject is no longer symptomatic and will be based on the reversibility of initiating factors (e.g., decreased oral intake, cold/flu, other illness)
SBP $\leq$ 90 mmHg* and/or the subject remains symptomatic after instituting oral and/or IV hydration and there is no other reason contributing to hypotensive event	Permanently Discontinue	The subject should be referred to urgent care or the emergency room Any other antihypertensives or other medications that could affect BP should be stopped, if feasible The use of IV angiotensin II or vasopressors should be considered in subjects that remain symptomatic and are hemodynamically unstable The subject will continue to be followed per protocol in the study. Follow-up for subjects that screen fail due to BP inclusion criteria (see Section 5.1) will not be necessary
SBP $>$ 180 mmHg* or DBP $>$ 110 mmHg*	Pause if BP elevation is thought to be transient, reversible and related to external initiating factors (e.g., stressful event) Permanently discontinue if no other reason contributing to hypertensive event	The suitability of the subject for continued dosing will be determined by the Investigator in consultation with the Sponsor Medical Monitor after the subject's BP has normalized Additional antihypertensive medication(s) may be added per Investigator and Sponsor Medical Monitor judgement if the subject has discontinued Study Drug. If the subject has not discontinued Study Drug, changes to the stable regimen of antihypertensives may result in withdrawal of the subject from the Treatment Period The subject will continue to be followed per protocol in the study. Follow-up for subjects that screen fail due to BP inclusion criteria (see Section 5.1) will not be necessary

\* BP measurements must be confirmed by a second measurement within 30 minutes

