### 8.5. Safety Monitoring Rules

Please refer also to the ‘Guidance for Investigator’ section of the Investigator’s Brochure.

For the purposes of the renal and platelet safety monitoring rules, Baseline is defined as:

- The last non-missing measurement prior to the first dose

In addition to the standard monitoring of clinical safety parameters, the following guidelines are provided for the monitoring of selected parameters chosen based on preclinical and clinical observations.

Confirmation Guidance: At any time during the study (Treatment or Post-Treatment Periods), the initial clinical laboratory results meeting the safety monitoring criteria presented below **must be confirmed** by performing measurements (ideally in the same laboratory that performed the initial measurement) on new specimens. All new specimen collections should take place as soon as possible (ideally within 3 days of the initial collection). For stopping rules, if the initial laboratory result is observed during the Treatment Period, the results from the retest **must be available** prior to administering the next dose of Study Drug (ISIS 757456 or placebo).

Re-dosing Guidance: Subjects with initial laboratory test values that reach a stopping rule must not be re-dosed until the re-test results are available. In general, subjects who do not meet the stopping rules based upon retest may continue dosing. However, the Investigator and the Sponsor Medical Monitor (or appropriately qualified designee) should confer as to whether additional close monitoring of the subject is appropriate. If any of the stopping criteria described below (refer to Section 8.6.1 to Section 8.6.5) are met, the subject will be permanently discontinued from further treatment with Study Drug (ISIS 757456 or placebo), evaluated fully as outlined below and in consultation with the Sponsor Medical Monitor or appropriately qualified designee, and will be followed up in accordance with Section 8.8 of the protocol.

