#### **8.5.5. Safety Monitoring for Blood Pressure**

Should a subject experience a BP measurement of  $\leq 90$  mmHg (systolic) a second measurement must be done within a 30-minute period. If the subject is symptomatic (i.e., dizziness, light-headedness, clammy skin, fatigue, blurry vision), at any point in the study, the subject should contact the Study Center immediately. If the confirmed SBP is  $\leq 90$  mmHg and/or the subject remains symptomatic, dosing of a subject with Study Drug will be paused. Oral and/or IV hydration should be instituted. The suitability of the subject for continued dosing will be determined by the Investigator in consultation with the Sponsor Medical Monitor after the SBP has normalized and/or subject is no longer symptomatic and will be based on the reversibility of initiating factors (e.g., decreased oral intake, cold/flu, other illness). If the subject remains symptomatic or if the SBP does not normalize Study Drug should be permanently discontinued (refer to Stopping Rules for BP Section 8.6.5).

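### Table 7 makes the stop and emergency referral for persistent hypotension depend on there being no other cause, a condition that Sections 8.5.5 and 8.6.5(1) do not contain

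*Combined protocol and SAP*

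**What the plan says.** Three places in the protocol govern a subject whose low pressure or symptoms do not respond to hydration.

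- **Section 8.5.5** pauses dosing, starts hydration, and then closes the pathway: "If the subject remains symptomatic or if the SBP does not normalize Study Drug should be permanently discontinued". It refers the reader to Section 8.6.5.
- **Section 8.6.5, item 1** covers confirmed systolic pressure of 90 mmHg or less and/or symptoms remaining after hydration. Its instruction is: "Study Drug should be permanently discontinued, and the subject should be referred to urgent care or the emergency room". It continues: "Any other antihypertensives or other medications that could affect BP should be stopped, if feasible".
- **Table 7**, the reference table at the end of Section 8.6.5, splits the pathway into two rows. The first row (pause) says: "If hypotension or symptoms of hypotension persist proceed to stopping rules below". The second row (permanent discontinuation) applies when systolic pressure is 90 mmHg or less and/or "the subject remains symptomatic after instituting oral and/or IV hydration and there is no other reason contributing to hypotensive event". The referral and the stopping of other pressure-lowering drugs are listed as actions in that second row.

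Section 8.5 adds a general rule on the stopping criteria: "refer to Section 8.6.1 to Section 8.6.5) are met, the subject will be permanently discontinued from further treatment with Study Drug".

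**The concern.** The second row of Table 7 carries a condition that the two text sections lack. Because the stop, the referral and the stopping of other pressure-lowering drugs all sit in that row, all three inherit the condition.

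This is a matter of patient safety. Every subject takes an ACE inhibitor or ARB plus one or two other antihypertensives, and the active arm adds a further agent acting on the same pathway. Section 2.2 names hypotension as a complication of combining such agents, and hypotension is named in the safety endpoint. A subject who is still hypotensive after fluids and also has an intercurrent illness is one for whom site staff need a clear instruction. A page titled as a reference table is a likely place for them to look during the event.

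**Working it through.** No arithmetic applies and the plan states no figure to reproduce. The check sets the rules side by side and follows three kinds of subject through them. Section 8.6.5(1) is read together with 8.5.5, so that both concern pressure or symptoms that persist after hydration.

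| Subject after hydration | Sections 8.5.5 and 8.6.5(1) | Table 7 |
|---|---|---|
| Recovered | Investigator and Medical Monitor decide on continued dosing | First row: same decision |
| Persistent, no other cause | Stop permanently, refer, stop other drugs if feasible | Second row: same actions |
| Persistent, contributing cause such as flu | Stop permanently, refer, stop other drugs if feasible | First row sends the subject on; second-row condition fails; no row applies |

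Text and table agree on the first two lines and part on the third.

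**Does the text supply the condition elsewhere?** Section 8.5.5 does mention initiating factors, in wording that the first row of Table 7 shares. The decision on continued dosing comes "after the SBP has normalized and/or subject is no longer symptomatic and will be based on the reversibility of initiating factors". That concerns resumption after recovery. The next sentence of 8.5.5 deals with non-recovery and does not mention cause.

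**Does the protocol write exemptions for cause into its rules elsewhere?** It does. The liver rules in 8.6.1 apply only where there is no alternative explanation. The high-pressure rule in 8.6.5(2) excepts transient events with reversible triggers, and the third row of Table 7 has a matching exception. For hypotension alone, the table has an exemption and the text has none.

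**Does the conflict depend on how the second row is parsed?** Its and/or construction allows two readings.

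1. The condition attaches to both limbs. Any persistent case with another cause then falls outside the row.
2. The condition attaches only to the symptom limb. Persistent systolic pressure of 90 mmHg or less then still triggers the stop and referral. The gap narrows to symptoms that persist with pressure above 90 mmHg and have another contributing cause.

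The second reading is the milder one, but it still leaves a condition that 8.5.5 and 8.6.5(1) do not contain.

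**Does Section 8.5 decide which prevails?** Its rule is triggered by meeting any of the criteria in 8.6.1 to 8.6.5. A persistent case with flu meets 8.6.5(1), and a narrower table row does not undo that. This favours the text for the permanent stop. Section 8.5 does not address the referral.

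**The case against.** The strongest reply is that the stop is already secured. Section 8.5 works on any criterion, 8.6.5(1) is met, and 8.5.5 points to Section 8.6.5 as a whole. Section 8.8 also requires discontinuation under any rule from 8.6.1 to 8.6.5, although its wording is about laboratory abnormalities. This largely stands for the stop, and it would be too strong to say that the documents leave that question wholly open. It does not reach the referral, and it does not help someone who consults only the table.

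A second reply is that the clause may be intended. The symptom limb of 8.6.5(1) does not require low pressure, so fatigue from flu at normal pressure would, read literally, force a permanent stop and emergency referral. The text may be the incomplete part. This is fair: the documents do not reveal the intent, and the fix has to allow for it.

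A reader might also infer that the table lets a subject with persistent hypotension be dosed again after a pause. The documents do not say that. The first row sends every persistent case to the stopping rules and never returns it to the sentence on continued dosing. What the table leaves is a gap, not a written permission to re-dose.

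Finally, Sections 8.5.5 and 8.6.5(1) are silent on cause and use advisory wording for the stop. They do not expressly say that cause is irrelevant. The point rests on the missing condition, not on an express statement.

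**Conclusion.** The inconsistency is real and the table is wrong as written against the text. For persistent hypotension or symptoms with a contributing cause, 8.6.5(1) directs a stop, a referral and, if feasible, withdrawal of other pressure-lowering drugs; Table 7 directs none of these. Section 8.5 favours the text for the stop and leaves the referral unaddressed.

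The size cannot be put as a number. The documents give no hypotension rates and do not define what counts as a contributing reason, so no count of subjects and no probability of re-dosing is claimed. No effect on the primary analysis is claimed either. The pause, the Medical Monitor consultation and ordinary clinical judgement limit the risk, but they do not supply the missing instruction. The conclusion assumes that some sites will act from the table, and it holds on either parsing of the second row, more narrowly on the second.

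**What to change.** Delete the clause about other contributing reasons from the second row of Table 7, so that the row matches Sections 8.5.5 and 8.6.5(1).

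If the sponsor did intend an exemption for cause, write it identically in 8.5.5, 8.6.5(1) and Table 7, and hold dosing until both systolic pressure and symptoms have resolved.

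In either case, keep the urgent-care or emergency referral for every persistent case, whatever its cause.

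The deletion is one clause, made by protocol amendment with a notice to sites; the alternative is a short wording change in three places. Neither adds procedures, visits or subjects.

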## 8.7. Adjustment of Dose and/or Treatment Schedule

If the safety profile warrants, and subjects have not met a stopping rule, Study Drug may be adjusted downward in consultation with the Sponsor Medical Monitor or designee.

## 8.8. Discontinuation of Study Drug

A subject must permanently discontinue study treatment for any of the following:

- The subject withdraws consent
- The subject experiences an AE that necessitates permanent discontinuation of Study Drug

- The subject develops laboratory test abnormalities that meet any of the stopping rules listed in Section 8.6.1 to Section 8.6.5
- The subject experiences an AE that necessitates unblinding of the Investigator

The reason for discontinuation of Study Drug must be recorded in the electronic Case Report Form (eCRF) and source documentation.

For subjects withdrawn for reasons other than withdrawal of consent every effort should be made to complete the early termination of study procedures and observations at the time of withdrawal (see [Appendix A](#)) and ideally within 2 weeks from the last dose of Study Drug.

## 8.9. Withdrawal of Subjects from the Study Procedures

Subjects must be withdrawn from study procedures for any of the following:

- Withdrawal of consent
- The subject is unwilling or unable to comply with the protocol

Other reasons for withdrawal of subjects from study procedures might include:

- At the discretion of the Investigator for medical reasons
- At the discretion of the Investigator or Sponsor for noncompliance
- Significant protocol deviation

All efforts will be made to complete and report the observations as thoroughly as possible up to the date of withdrawal. All information, including the reason for withdrawal from study, must be recorded in the eCRF.

Any subject who withdraws consent to participate in the study will be removed from further treatment and study observation immediately upon the date of request. These subjects should be encouraged to complete the early termination study procedures and observations at the time of withdrawal ([Appendix A](#)).

For subjects withdrawn for reasons other than withdrawal of consent every effort should be made to complete the early termination of study procedures and observations at the time of withdrawal (see [Appendix A](#)) and ideally within 2 weeks from the last dose of Study Drug.

## 8.10. Concomitant Therapy and Procedures

The use of concomitant therapies or procedures defined below must be recorded on the subject's eCRF. AEs related to administration of these therapies or procedures must also be documented on the appropriate eCRF.

### 8.10.1. Concomitant Therapy

A concomitant therapy is any non-protocol specified drug or substance (including over-the-counter medications, herbal medications and vitamin supplements) administered between Screening and the Post-Treatment Evaluation Period.

### **Allowed Concomitant Therapy**

Any other medications deemed necessary by the Investigator are allowed except those listed in the disallowed concomitant therapy.

### **Disallowed Concomitant Therapy**

The following are disallowed concomitant therapies:

- Other medications for the treatment of HTN (e.g., clonidine, guanfacine, guanabenz, alpha-methyldopa, hydralazine, minoxidil, diazoxide, renin inhibitors)
- Medications that may cause hyperkalemia (e.g., cyclosporine or tacrolimus, pentamidine, trimethoprim-sulfamethoxazole, all heparins)
- Oral or SC anticoagulants (e.g., warfarin, rivaroxaban, apixaban, lovenox, heparin)
- Organic nitrate preparations (e.g., nitroglycerin, isosorbide mononitrate, isosorbide dinitrate, or pentaerythritol)
- Sildenafil, tadalafil, vardenafil
- Potassium sparing diuretics (e.g., eplerenone, spironolactone, amiloride, triamterene)

Changes to the stable regimen of antihypertensives allowed at Screening may result in withdrawal of the subject from the Treatment Period.

#### **8.10.2. Concomitant Procedures**

A concomitant procedure is any therapeutic intervention (e.g., surgery/biopsy, physical therapy) or diagnostic assessment (e.g., blood gas measurement, bacterial cultures) performed between Screening and the Post-Treatment Evaluation Period.

#### **8.11. Treatment Compliance**

Compliance with treatment dosing is to be monitored and recorded in the eCRF by Study Center staff.

## **9. SERIOUS AND NON-SERIOUS ADVERSE EVENT REPORTING**

### **9.1. Sponsor Review of Safety Information**

Safety information will be collected, reviewed, and evaluated by the Sponsor or designee in accordance with the applicable Ionis and/or designee SOPs throughout the conduct of the clinical trial.

### **9.2. Regulatory Requirements**

The Sponsor is responsible for regulatory submissions and reporting to the Investigators of SAEs including SUSARs per the International Conference on Harmonization (ICH) guidelines E2A and ICH Good Clinical Practice (GCP). Country-specific regulatory requirements will be followed in accordance with local country regulations and guidelines.

IRBs will be notified of any SAE according to applicable regulations.

The Sponsor will evaluate the available information for all reported SAEs and decide if there is a reasonable possibility that the Study Drug (ISIS 757456 or placebo) caused the AE and, therefore, meets the definition of a SUSAR.

Appropriate personnel at the Sponsor will unblind SUSARs for the purpose of regulatory reporting. The Sponsor will submit SUSARs to Regulatory Agencies in blinded or unblinded fashion according to local law. The Sponsor will submit SUSARs to Investigators in a blinded fashion.

For the purpose of regulatory reporting of SUSARs, there are no “expected” AEs in this study population. For Study Drug (ISIS 757456 or placebo) “expected” AEs, refer to the Investigator’s Brochure.

### **9.3. Definitions**

#### **9.3.1. Adverse Event**

An AE can be any unfavorable and unintended sign (including an abnormal laboratory finding, for example), symptom, or disease temporally associated with the use of medicinal (investigational) product, whether or not the AE is considered related to the medicinal (investigational) product.

An AE can therefore be any of the following:

- Any unfavorable and unintended sign (including an abnormal laboratory finding), symptom, or disease temporally associated with the use of a medicinal product, whether or not considered related to the medicinal product
- Any new disease or exacerbation of an existing disease (a worsening in the character, frequency, or severity of a known condition)
- Recurrence of an intermittent medical condition (e.g., headache) not present at Baseline
- Any deterioration in a laboratory value or other clinical test (e.g., ECG, X-ray) that is associated with symptoms or leads to a change in study treatment or concomitant treatment or discontinuation from Study Drug

AEs that are related to a protocol-mandated intervention, including those that occur prior to assignment of study treatment (e.g., screening invasive procedures such as biopsies).

#### **9.3.2. Adverse Drug Reaction and Suspected Unexpected Adverse Drug Reaction**

##### **Adverse Drug Reaction (ADR)**

In the *pre-approval* clinical experience with a new medicinal product or its new usages, particularly as the therapeutic dose(s) may not have been established, ADR is defined as follows:

All noxious and unintended responses to a medicinal product related to any dose should be considered ADRs.

The phrase "responses to a medicinal product" means that a causal relationship between the medicinal product and the AE has been determined by the Sponsor as at least a reasonable possibility, i.e., the relationship cannot be ruled out.

